### For primary efficacy endpoint

- Presence of CNV in the fellow eye (yes; no)
- Baseline GA lesion area ( $< 7.5 \text{ mm}^2$  or  $\geq 7.5 \text{ mm}^2$ )

### For key secondary, secondary, and exploratory endpoints

- Presence of CNV in the fellow eye (yes; no)
- Baseline GA lesion area ( $< 7.5 \text{ mm}^2$  or  $\geq 7.5 \text{ mm}^2$ )
- Baseline value of the endpoint

Of note, the randomization stratification factors were assessed at the screening visit. In the event of a change in status in the GA lesion area between the screening visit and the baseline visit (i.e., GA lesion area  $< 7.5 \text{ mm}^2$  at screening to  $\geq 7.5 \text{ mm}^2$ ) then the baseline status will be used.

If a statistical model is not directly specified and if necessary, data will be analyzed with the following approaches:

- For continuous endpoints, the MMRM analysis described for the primary endpoint in Section 6.2.2.
- For categorical or ordinal variables, a Cochran Mantel Haenszel (CMH) test with the baseline category status, presence of CNV in the fellow eye (yes or no), and baseline GA lesion area ( $< 7.5 \text{ mm}^2$  or  $\geq 7.5 \text{ mm}^2$ ) as stratification factors.

### 6.1. Estimands

The primary scientific research question of this study is to assess the effect of pegcetacoplan compared with that of sham at Month 12 regarding the impact on GA lesion progression under-real-life conditions following the ITT principal.

The primary estimand in the study is defined through the following 5 attributes:

- **Population:** GA subjects defined through inclusion and exclusion criteria in the mITT population.
- **Treatment conditions:** The treatment regimen of interest in this study is PM, PEOM, and Sham.
- **Variable (or endpoint):** Change in total area of GA lesions in the study eye from baseline measured by FAF to Month 12.
- **Strategy for addressing intercurrent events:** See description of intercurrent events below.
- **Population-level summary:** Difference in mean change of GA lesion from baseline to Month 12 between pegcetacoplan and sham groups according to MMRM analysis.

The intercurrent events that will be considered are:

- Treatment discontinuation
- Lost to follow up
- Withdrawal from the study

The intercurrent events will be handled with a treatment policy strategy whereby any measured value will be used as is. Missing data resulting from these intercurrent events will be handled implicitly within the MMRM analysis that assumes missing at random.

The key secondary estimands will be defined and analyzed in the similar fashion as the primary estimand. The primary and key secondary estimands are summarized in [Table 2](#).

**Table 2: Estimands of Study**

Estimand	Definition	Attributes			
		A: Population	B: Variable (or endpoint)	C: Strategy for addressing intercurrent event	D: Population-level summary
		Main Analyses			
Primary	The effect of pegcetacoplan compared to sham at Month 12 in impact on GA progression	mITT	Change in the total area of GA lesions from baseline measured by FAF to Month 12	
 
Treatment policy strategy for subjects who discontinue treatment, are lost to follow-up, or withdraw from the study
 
	Difference in mean change of GA lesion from baseline at Month 12 between pegcetacoplan and sham groups based on MMRM analysis
Key Secondary #1	The effects of pegcetacoplan compared to sham at Month 24 in impact on macular functional response	mITT	Change in mean threshold sensitivity of all points from baseline to Month 24	
 
Treatment policy strategy for subjects who discontinue treatment, are lost to follow-up, or withdraw from the study
 
	Difference in mean change in mean threshold sensitivity of all points from baseline at Month 24 between pegcetacoplan and Sham groups based on MMRM analysis
Key Secondary #2	The effects of pegcetacoplan compared to sham at Month 24 in impact on monocular maximum reading speed	mITT	Change in monocular maximum reading speed from baseline to Month 24	
 
Treatment policy strategy for subjects who discontinue treatment, are lost to follow-up, or withdraw from the study
 
	Difference in mean change in monocular maximum reading speed from baseline at Month 24 between pegcetacoplan and Sham groups based on MMRM analysis
Key Secondary #3	The effects of pegcetacoplan compared to Sham at Month 24 in impact on mean FRI Index score	mITT	Change in mean FRI Index score from baseline to Month 24	
 
Treatment policy strategy for subjects who discontinue treatment, are lost to follow-up, or withdraw from the study
 
	Difference in mean change in mean FRI Index score, from baseline at Month 24 between pegcetacoplan and sham groups based on MMRM analysis

**Table 2: Estimands of Study**

Estimand	Definition	Attributes			
		A: Population	B: Variable (or endpoint)	C: Strategy for addressing intercurrent event	D: Population-level summary
Key Secondary #4	The effects of pegcetacoplan compared to Sham at Month 24 in impact on NL-BCVA score	mITT	Change in NL-BCVA score from baseline to Month 24	
 
Treatment policy strategy for subjects who discontinue treatment, are lost to follow-up, or withdraw from the study
 
	Difference in mean change of NL-BCVA score from baseline at Month 24 between pegcetacoplan and sham groups based on MMRM analysis

## 6.2. Analyses of Primary Efficacy Endpoint

The primary efficacy endpoint is change from baseline to Month 12 in total area of GA lesion(s) in the study eye (in  $\text{mm}^2$ ) based on FAF.

The hypotheses of interest and Type I error management for analyses of the primary endpoint are specified below and take precedence over that specified in the study protocol.

For the primary efficacy endpoint, sensitivity analyses (Section 6.2.3), supplementary analyses (Section 6.2.4), and subgroup analyses (Section 6.2.5) will be performed.

All analyses of the first 12 months will be performed at the Month 12 reporting as well as repeated at the final reporting. Unless otherwise specified, at the time of the final reporting, all analyses will be repeated using the data for the full 24 months.

### 6.2.1. Type I Error Management

The null hypotheses for the primary efficacy endpoint are the following:

- $H_{1a}$ : There is no difference between PM and Sham in mean change from baseline to Month 12 in total area of GA lesion(s) in the study eye (in  $\text{mm}^2$ ) based on FAF for the mITT set.
- $H_{1b}$ : There is no difference between PEOM and Sham in mean change from baseline to Month 12 in total area of GA lesion(s) in the study eye (in  $\text{mm}^2$ ) based on FAF for the mITT set.

For hypothesis testing of the primary efficacy endpoint, type I error will be controlled using a fixed sequencing approach by testing the two hypotheses ( $H_{1a}$  and  $H_{1b}$ ) sequentially, beginning with  $H_{1b}$ . All hypothesis tests for the primary endpoint will be based on a two-sided alpha level of 0.05. The alpha will be adjusted in accordance with the protocol for the number of Data Monitoring Committee (DMC) unmasked reviews prior to the Month 12 analysis timepoint (i.e., 4 DMC unmasked reviews prior to Month 12: 2-sided alpha level = 0.0496). Testing for statistical significance proceeds to  $H_{1b}$  only if  $H_{1a}$  is statistically significant. The study will be considered positive if the first hypothesis ( $H_{1a}$ ) is rejected.

### 6.2.2. Main Analysis of Primary Efficacy Endpoint

The primary endpoint will be analyzed in the mITT population with subjects grouped according to the treatment assigned at randomization.

A MMRM model will be used to analyze the primary endpoint. The analysis model will include treatment (PM, PEOM, sham), presence of choroidal neovascularization in the fellow eye at baseline (Yes, No) and baseline GA lesion area ( $< 7.5 \text{ mm}^2$  or  $\geq 7.5 \text{ mm}^2$ ) as fixed effects, time (study month, categorical) as a factor, the time  $\times$  treatment interaction term, and the baseline GA lesion area ( $< 7.5 \text{ mm}^2$  or  $\geq 7.5 \text{ mm}^2$ )  $\times$  time interaction term. The least square [LS] mean change from baseline to Month 12 will be estimated from the model for each of three arms as well as the comparisons of each of the three arms to each other. For other time points of interest, LS mean change from baseline will be estimated and compared between treatments. For each estimated LS mean, the corresponding 95% CI will be presented based on the model. For the comparison of the LS means, the corresponding 95% CI and the 2-sided P-value along with the percentage difference (difference in LS means between the arms/the comparison group LS mean) will be

presented. A common unstructured covariance matrix will be used to model the within-subject errors, the sandwich estimator (Diggle, Liang, and Zeger 1994) will be used to estimate the standard errors of the fixed effects parameters, and the degrees of freedom will be partitioned into between-subject and within-subject portions. If there are convergence problems with the model, then a heterogeneous autoregressive (1) covariance matrix will be used. If convergence problems still exist, an autoregressive (1) covariance matrix will be used. The LS mean of the change from baseline in the total area of GA lesion(s)  $\pm$  the standard error will be plotted over time by treatment group.

The observed values for the total area of GA lesion(s) will be summarized by treatment group and visit for both the study and the fellow eye. Summaries will present the descriptive statistics for baseline, absolute values and change from baseline data by visit.

The mean change from baseline in the total area of GA lesion (s) in the study eye  $\pm$  the standard error will be plotted over time by treatment group.

All GA lesion (s) size data will be listed for the ITT set.

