### 3.2. Randomization

Subjects will be randomized 2:2:1:1 using a web-based randomization system to receive treatment with PM, PEOM, SM or SEOM, respectively.

The randomization scheme will be maintained by the Sponsor, or designee. Subject randomization will be stratified by GA lesion area at screening based on assessment from the reading center ( $< 7.5 \text{ mm}^2$ ;  $\geq 7.5 \text{ mm}^2$ ) and presence of CNV in the fellow eye (yes; no).

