### **6.2.5. Subgroup Analyses of Primary Efficacy Endpoint**

Subgroup analyses will be performed to evaluate the consistency of the primary analysis results across subgroups defined by demographic and baseline characteristics. Analyses will be performed for the primary efficacy endpoint (change from baseline in total area of GA lesion(s) in the study eye at Month 12) for each of the following subgroups (as appropriate per actual subgroup sample size, levels with low sample size may be pooled to allow for an analysis to be conducted):

- Age Group (<75 years, 75 to <85 years, ≥85 years)
- Sex (male, female)
- Race (White, Black or African American, Asian, American Indian or Alaskan Native, Native Hawaiian or other Pacific Islander, multiple, unknown)
  - Note: If most subjects (e.g., >90%) are of a single race, this analysis will not be conducted.
- Geographic Region (United States vs Rest of World)
- Subgroups indicative of disease severity at baseline
  - Study eye baseline GA lesion size (<7.5 mm^2; ≥7.5 mm^2)
  - Study eye baseline GA lesion size categories (approximately tertiles based on APL2-303/304 combined data\*)
  - Study eye baseline NL-BCVA categories (≥70, ≥60 - <70, ≥35 - <60, <35 ETDRS letters)
  - Study eye baseline NL-BCVA categories (<60 vs. ≥60 ETDRS letters)
  - Study eye baseline LL-BCVA categories (approximately tertiles based on APL2-303/304 combined data\*)
  - Study eye baseline monocular maximum reading speed categories (approximately tertiles based on APL2-303/304 combined data\*)
  - Baseline FRI Level (1,2,3,4)
  - Study eye mean threshold sensitivity of all points categories (approximately tertiles)
- Subgroups associated with GA progression
  - Study eye baseline GA focality (multifocal, unifocal)

- Study eye baseline GA lesion location (subfoveal involvement, without subfoveal involvement)
- Baseline GA laterality (bilateral GA (with or without CNV in fellow eye) vs. Study eye GA Only)
- Baseline CNV in fellow eye (Fellow eye CNV vs. No fellow eye CNV)
- Study eye baseline LLD categories (<20 vs.  $\geq$  20 ETDRS letters)
- Study eye baseline LLD categories (approximately tertiles based on the APL2-303/304 combined data\*)
- Study eye baseline NL-BCVA (<60 vs.  $\geq$ 60 ETDRS letters) and LLD (<20 vs.  $\geq$  20 ETDRS letters) combinations

\*Approximately tertiles will be specified consistently across the APL2-303/304 studies to the nearest clinically relevant level.

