### 1.2.1. Mixed Effect Model for Repeated Measure

```
-----  
* Read Analysis data  
-----  
* In this example, repeated measures are available at  
* avisitn = 0.5 (baseline), 2 (Month 2),  
* 6 (Month 6), and 12 (Month 12)  
-----;
```

```
data ga;  
  set adam.adga;  
  if paramcd = 'SEGAORG' and  
    avisitn in (0.5, 2, 6, 12) and  
    ANL01FL = 'Y';  
  
  * trtan (actual treatment[number])  
  * 1 = APL-2 Monthly  
  * 2 = APL-2 Every Other Month  
  * 3 = pooled Sham group;  
  if trtan in (4,5) then trtan = 3;  
  
  * trt01 are trt02 are used in multiple imputation  
  * trt01 = 1 if Sham group  
  * trt02 = 1 if APL2 Monthly group  
  * trt01 = trt02 = 0 for APL2 EOM group;  
  if trtan = 3 then trt01= 1; else trt01 = 0;  
  if trtan = 1 then trt02= 1; else trt02 = 0;  
  
  * avisitc will be used in PROC TRANSPOSE;  
  if avisitn = 0.5 then avisitc = '00'; * Baseline;  
  if avisitn = 2 then avisitc = '02'; * Month 2;  
  if avisitn = 6 then avisitc = '06'; * Month 6;  
  if avisitn = 12 then avisitc= '12'; * Month 12;  
run;
```

```
*****;  
*** MAIN ANALYSIS using MMRM ***;  
*****;
```

```
proc mixed data=ga method=reml covtest empirical;  
  where avisitn NE 0.5; * exclude rows for baseline;  
  * cnv (CNV in the fellow eye)  
  * 0 = No  
  * 1 = Yes;  
  *base cat (baseline lesion size (<7.5 vs. ≥ 7.5));  
  class trtan cnv avisitn usubjid base_cat;  
  model chg = trtan cnv base_cat avisitn trtan*avisitn base_cat*avisitn  
  /cl;
```

```
repeated avisitn / subject=usubjid type=un r;  
lsmeans trtan*avisitn/pdiff cl e alpha=.05;  
ods output diffs= diff1 LSMeans= LSMean1;  
run;
```

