### 1.2.3. Rate of Change Models

```
*****;
*** Rate of Change analyses ***;

* In this example, repeated measures are available at
* avisitn = 0 (baseline), 2 (Month 2), 4 (Month 4)
* 6 (Month 6), 8 (Month 8), 10 (Month 10) and 12 (Month 12)
*
* AVAL is the actual GA lesion measurement at the corresponding visit * for
the study eye from ADGA.
* SGALESAT is the GA lesion size (categorical) at baseline
* FCNVAT is the fellow eye CNV status at baseline
* TR01PG2N is the pooled treatment group (1 = PM, 2 = PEOM, 3 = Sham)
* T is equivalent to AVISITN
*
* The data is read in from ADGA
*****;
```

```
proc mixed data=ga method=reml covtest empirical;
```

```
class subjid TR01PG2N FCNVAT SGALESAT t;
model aval = SGALESAT TR01PG2N avisitn TR01PG2N * avisitn
          SGALESAT*avisitn FCNVAT/cl solution;
repeated t /type=un sub=subjid r ;

**Month 6;
estimate 'PM Month 0 to 6 slope' TR01PG2N*avisitn 6 0 0
          avisitn 6 SGALESAT*avisitn 3 3 /cl;
estimate 'PEOM Month 0 to 6 slope' TR01PG2N*avisitn 0 6 0
          avisitn 6 SGALESAT*avisitn 3 3 /cl;
estimate 'Sham Month 0 to 6 slope' TR01PG2N*avisitn 0 0 6
          avisitn 6 SGALESAT*avisitn 3 3 /cl;

estimate 'Month 0 to Month 6 Difference in slope PM - Sham'
          TR01PG2N*avisitn 6 0 -6 /cl;
estimate 'Month 0 to Month 6 Difference in slope PEOM - Sham'
          TR01PG2N*avisitn 0 6 -6 /cl;
estimate 'Month 0 to Month 6 Difference in slope PM - PEOM'
          TR01PG2N*avisitn 6 -6 0 /cl;

**Month 12;
estimate 'PM Month 6 to 12 slope' TR01PG2N*avisitn 6 0 0
          avisitn 6 SGALESAT*avisitn 3 3 /cl;
estimate 'PEOM Month 6 to 12 slope' TR01PG2N*avisitn 0 6 0
          avisitn 6 SGALESAT*avisitn 3 3 /cl;
estimate 'Sham Month 6 to 12 slope' TR01PG2N*avisitn 0 0 6
          avisitn 6 SGALESAT*avisitn 3 3 /cl;

estimate 'Month 6 to 12 Difference in slope PM - Sham'
          TR01PG2N*avisitn 6 0 -6 /cl;
estimate 'Month 6 to 12 Difference in slope PEOM - Sham'
          TR01PG2N*avisitn 0 6 -6 /cl;
estimate 'Month 6 to 12 Difference in slope PM - PEOM'
          TR01PG2N*avisitn 6 -6 0 /cl;

ods output diffs= diff2 LSMeans= LSMean2 CovParms = COV2
          estimates = estimates2;

**Month 0 to 12;
estimate 'PM Month 0 to 12 slope' TR01PG2N*avisitn 12 0 0
          avisitn 12 SGALESAT*avisitn 6 6 /cl;
estimate 'PEOM Month 0 to 12 slope' TR01PG2N*avisitn 0 12 0
          avisitn 12 SGALESAT*avisitn 6 6 /cl;
estimate 'Sham Month 0 to 12 slope' TR01PG2N*avisitn 0 0 12

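### Fellow-eye CNV, a randomization stratum, has no time interaction in the primary GA-area MMRM or the slope models, so it adjusts Month 12 growth only slightly; the loss is small precision, not bias

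*SAP*

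**What the plan says.** SAP 3.2 stratifies randomization on lesion size and on "presence of CNV in the fellow eye (yes; no". SAP 6.2.2 describes the primary model: "The analysis model will include treatment (PM, PEOM, sham), presence of choroidal neovascularization in the fellow eye at baseline (Yes, No". CNV is a fixed effect there. The model also includes treatment × time and lesion-size category × time, but no CNV × time. The code in SAP Appendix 1.2.1 agrees: "model chg = trtan cnv base_cat avisitn trtan*avisitn base_cat*avisitn". The same analysis model is run on the imputed datasets in Appendix 1.2.2. Protocol 12.7.1 also has CNV as a main effect only; the SAP added the lesion-size interaction without a matching CNV term.

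On covariance, SAP 6.2.2 says: "A common unstructured covariance matrix will be used to model the within-subject errors". The fallbacks are heterogeneous AR(1) and then: "If convergence problems still exist, an autoregressive (1) covariance matrix will be used".

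The rate-of-change models (SAP 6.2.4.3) take lesion area itself as the response. The code in Appendix 1.2.3 begins "model aval = SGALESAT TR01PG2N avisitn TR01PG2N * avisitn" and goes on to cross lesion category with time; CNV stands alone. The piecewise model does the same.

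Among factors tied to GA progression, SAP 6.2.5 lists the subgroup "Baseline CNV in fellow eye (Fellow eye CNV vs. No fellow eye CNV".

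**The concern.** The primary response is change from baseline, which starts near zero for everyone. A factor that speeds or slows growth therefore has an effect that builds over the year, and a constant has the wrong shape for it. With an unstructured covariance, that constant is set mainly by the early visits, where variance is low and the CNV effect is still small. Most of any Month 12 effect then stays in the residual, and a chance CNV imbalance between arms is only partly adjusted.

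In the slope models the CNV term shifts the level of lesion area but not its growth, and growth is what those models compare.

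At stake is some precision that the stratified design could deliver, and consistent handling of the two strata.

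**Working it through.** **Plan's own power.** Inputs from SAP 3.4 and Table 1: means 1.70 (PEOM) and 2.13 (sham), SD 1.50, 200 per group. The difference is 0.43, SE = 1.5 × √(2/200) = 0.150, ratio 2.867. A one-way ANOVA contrast (597 df) at alpha 0.0495 gives 81.5% for PEOM and 99.2% for PM, matching Table 1. The normal approximation at alpha 0.0496 (SAP 6.2.1; critical value 1.964) gives 81.7% for PEOM, the base for the comparison below.

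**Share of the Month 12 CNV effect recovered.** Let V be the 6 × 6 covariance of change at Months 2, 4, …, 12, and let the true CNV effect be D = d × (1/6, 2/6, …, 1). The fitted constant tends to (1′V⁻¹D)/(1′V⁻¹1); dividing by d gives the share f. The documents give no visit covariance or measurement error, so both are assumed, with the Month 12 SD of change held at 1.5.

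For a random slope plus measurement error of SD s, f = (7/12)/(1 + 70q), where q = [(2.25 − 2s²)/144]/s². With s = 0.3, q = 0.014375/0.09 = 0.160 and f = 0.583/12.18 = 4.8%.

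| Assumed growth | s = 0.1 | s = 0.3 | s = 0.5 |
|---|---|---|---|
| Random slope | 0.5% | 4.8% | 13.2% |
| Half slope, half random walk | 9.6% | 13.4% | 20.2% |
| Random walk | 17.1% | 20.2% | 25.8% |

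Under homogeneous AR(1) the weights are symmetric in time, so f = 7/12 = 58% at any autocorrelation. Under heterogeneous AR(1) with SD proportional to time and autocorrelation 0.8 to 0.95, f is 10% down to 3%.

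**Check by simulation.** Trials of 600 subjects with random-slope growth, a true Month 12 CNV effect of 0.40 mm², and unstructured fits with sandwich SEs, 25 trials per setting:
- The constant averaged 0.004 to 0.053, that is 1% to 13% of the true effect.
- With CNV × visit, the Month 12 effect averaged 0.40 to 0.43.
- The SE of PM minus sham fell by about 1%, for example from 0.151 to 0.150.

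**Slope models.** Every between-subject factor that has a slope in these models also has its own intercept. Adding a further intercept-only term therefore leaves the GLS slope estimates unchanged when data are complete and the covariance is given. In one simulated dataset with CNV prevalence deliberately set at 50%, 40% and 30% across PM, PEOM and sham, the PM minus sham slope was −0.5172 mm² per year with and without the CNV main effect. With CNV × time it was −0.6266.

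**Precision at stake.** The variance share of CNV is p(1 − p)d²/2.25, with prevalence p and effect d both assumed.
- p = 0.2, d = 0.2: 0.0064/2.25 = 0.28%; SD 1.498; ratio 2.871; power 81.8%.
- p = 0.4, d = 0.6: 0.0864/2.25 = 3.84%; SD 1.471; ratio 2.923; power 83.1% (83.2% at alpha 0.05).

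These assume that none of the effect is removed now and all of it would be afterwards, so they slightly overstate the gain.

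**Imbalance.** An assumed 5-point CNV imbalance with a 0.4 mm² effect shifts the Month 12 difference by at most 0.05 × 0.4 = 0.02 mm², against an SE of 0.15.

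**The case against.** The strongest reply is that nothing of consequence changes. PM versus sham, which decides whether the study is positive, already has 99.2% power. The PEOM gain is at most about 1.5 points (83.1 − 81.7 = 1.4 from rounded figures), and reaching it takes a CNV effect of 0.6 mm², more than the whole planned PEOM effect of 0.43. The documents give no CNV effect on growth, no prevalence and no visit covariance; SAP 6.2.5 gives neither size nor direction. If CNV does not affect growth, nothing is lost. The main-effect adjustment was prespecified in the protocol, and the planned CNV subgroup analysis fits the MMRM within each stratum. All of this stands, and it sets the priority. The subgroup fits do not, however, give an overall Month 12 contrast adjusted for CNV.

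A reader might infer that the primary result is biased, or that its type I error is at risk. The documents do not support that. Randomization is stratified on CNV, and leaving its effect in the residual is slightly conservative.

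A reader might also look to dropout. In Phase 2 (Protocol 4.1.4), new active CNV arose in 25 of 165 pegcetacoplan subjects and 1 of 81 sham subjects, and 17 of those 25 had a fellow-eye history of neovascular AMD. That makes differential discontinuation by CNV conceivable but does not show it. The unstructured MMRM also conditions on each subject's earlier lesion changes, and the imputation code in Appendix 1.2.2 includes CNV in its visit-by-visit regressions.

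Finally, a reader might extend the point to the key secondary models in SAP 6.3.2. No magnitude has been shown there: the mechanism was worked out only for lesion area, and no covariance was evaluated for the functional measures.

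**Conclusion.** The point holds for the GA-area models as an optional improvement. The asymmetry between the two strata is exact in both text and code. If CNV's effect on change grows linearly, the constant term removes about 0.5% to 26% of it at Month 12 under the assumed covariances with an unstructured matrix, and about 58% under the AR(1) fallback. It would therefore be too strong to say that the adjustment is always close to nothing. For the slope models, the statement that the slope differences are unadjusted rests on complete data and a given covariance, and on no assumed effect size.

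The cost of leaving the plan as it is would be a slightly wide standard error. On the assumed effects and prevalences, PEOM power would rise by roughly 0.1 to 1.5 points if the term were added.

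**What to change.** Before unmasking for the Month 12 analysis:
- Add CNV in the fellow eye × visit to the primary MMRM in SAP 6.2.2 and Appendix 1.2.1, and to the analysis model for the imputed data in Appendix 1.2.2. With six post-baseline visits this costs 5 degrees of freedom.
- Add CNV × time to the slope model, and CNV × time plus CNV × the spline term to the piecewise model (SAP 6.2.4.3, Appendix 1.2.3), matching the lesion-size stratum.

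No new data are needed and the estimand does not change. The cost is SAP wording and a few model terms. If treatment codes have already been opened, keep the planned primary model and report the extended one as a labelled post hoc sensitivity analysis.
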